#### **Assessment of Depth of Anesthesia through BIS monitoring**

We will measure depth of anesthesia during surgery using the Bispectral Index Monitor (BIS), which is an FDA-approved device to measure processed electroencephalogram signals. Two adhesive pads will be placed on the patient's forehead during surgery for this monitoring.

**Cardiopulmonary Bypass:** A 40- $\mu$ m or smaller filter will be placed in the CPB circuit. Blood flow during CPB will be maintained between 2.0 and 2.4 L/min/m^2 using nonpulsatile flow.

Nasopharyngeal temperature will be measured during surgery and the temperature nadir recorded. In addition to continuous in-line monitoring, arterial blood gases will be recorded 30 min after the start of CPB and every 60 min thereafter. The patients will be managed using a-stat pH management. Hemoglobin will kept >8.0 g/dL with transfusion of packed red blood cells. Blood glucose will be measured at the onset of CPB and at least every 60 min thereafter. Blood glucose will be managed per routine standard of care. Rewarming will be at an arterial inflow temperature of  $\leq$ 37°C. Nasopharyngeal temperature will not exceed 36°C. Surgical field CO2 insufflation will be performed. Cardiotomy suction will be returned to the CPB circuit after being processed with a cell saver device for patients undergoing CABG surgery or directly to the CPB circuit for open chamber procedures, as is our usual practice.

**Perioperative Blood Pressure Monitoring and Recording:** A decrease in arterial blood pressure that occurs any time preoperatively could confound analysis of the data. Blood pressure will be monitored using standard operating room and ICU monitors. Transducers will be placed level with the right atrium and zeroed to atmospheric pressure before the start of anesthesia, before the start of CPB, and after separating from CPB. Blood pressure will be recorded continuously during surgery and recorded on a computer interfaced with the operating room hemodynamic monitor (using ICM+ software, see Cerebral Autoregulation Monitoring and CBF Autoregulation Measurements). Computerized medical record systems will record arterial pressure every 15 min in the ICU. Study personnel will review these medical records daily for the duration of the ICU admission. The number of hypotensive episodes (mean arterial pressure <70 mmHg) will be recorded to adjust for the effect of this potential confounding variable on the primary outcomes. The dose and duration of any vasoconstrictor or vasodilator drugs given during surgery and in the ICU will be recorded.

[figure not shown]
The patients will be visited on the postoperative ward daily by members of the surgical team to evaluate for adverse events, cardiac arrhythmias, and other events necessitating medical intervention, including hypotension or other complications.

**Perioperative Variables:** The patients will receive routine institutional perioperative care that includes continuous arrhythmia monitoring with telemetric ECG after surgery. Postoperative variables, including complications that affect organ systems, will be collected during the hospitalization. Patients will undergo 12-lead ECGs before surgery and on arrival to the ICU after surgery as well as for the first 3 postoperative days. The definition of myocardial infarction will be a new Q-wave >0.04 sec and/or >1/3 the height of the R-wave. Data sheets for each patient will be completed to denote no myocardial infarction or Q-wave myocardial infarction. The data will then be entered into the study database.

## Autoregulation Monitoring

CBF autoregulation will be monitored continuously by members of the investigative team. The patient's forehead will be cleansed with the supplied alcohol sponge and wiped dry. Then, two Foresight monitoring electrodes will be calibrated, as specified by the manufacturer, and placed on the patient's forehead. The electrodes will be attached to a Fore-Sight cerebral oximeter (CasMed, Branford, CTI) specially equipped with an output signal for this project. We will perform TCD monitoring (DWL, Compumedics DWL, El Paso, TX) of the right and left middle cerebral arteries using two 2.5-MHz transducers fitted on a headband and positioned over the temporal bone windows to obtain bilateral continuous measurement of baseline velocity. Depth of insonation will be varied between 35 and 52 mm until representative spectral middle cerebral artery flow is identified.

Arterial pressure from an indwelling cannula (started for clinical indication), along with TCD signals from the middle cerebral arteries and the near-infrared spectroscopy signals, will be sampled with an analog-to-digital converter using ICM+ software at 58 Hz.31-37 Digital rScO2 signals from the NIRS monitor will be transferred directly to a laptop computer. Blood pressure, TCD, and rScO2 signals will then be time integrated as non-overlapping 10-sec mean values, equivalent to applying a moving average filter with a 10-sec time window and re-sampling at 0.1 Hz. This operation eliminates high-frequency noise from the respiratory and pulse frequencies, according to the Nyquist theorem, allowing detection of oscillations and transients that occur below 0.05 Hz. A continuous, moving Pearson correlation coefficient will be calculated between mean arterial pressure and TCD CBF velocity of the middle cerebral arteries, rendering the variable mean velocity index (Mx). Similar methods will be performed to calculate the Pearson correlation coefficient between mean arterial pressure and cerebral oximetry signals, rendering the variable cerebral oximetry index, and between mean arterial pressure and relative total hemoglobin signals, generating the hemoglobin volume index (see Cerebrovascular Reactivity Measured by Nearinfrared Spectroscopy). Consecutive, paired, 10-sec averaged values from 300-sec duration will be used for each calculation, incorporating 30 data points for each index.35,37 Mx and COx values for each patient will be placed into 5 mmHg MAP bins and displayed on the laptop computer (**Figs. 3 and 6**). When MAP is within the limits of CBF autoregulation, Mx and COx approach zero, but when MAP is

**Fig 6.** Dysregulated pattern when COx is >0.3 at all MAPs. In this patient optimal MAP is 70-75 mmHg. Note, the top panel is the MAP time series. The y-axis on the remaining graphs is left and right COx, respectively, on a scale of 0 to 1.0. The xaxis is MAP in 5 mmHg bins.

outside the limits of autoregulation,  $M_x$  and  $CO_x$  approach 1, indicating that CBF is blood pressure dependent. Based on our prior studies, we designate the LLA as the highest MAP associated with  $M_x \geq 0.2$  or  $CO_x \geq 0.3$ . These values are within the range found to be associated with poor outcome after traumatic brain injury and adverse outcomes after cardiac surgery. In about 20% of patients, impaired autoregulation is observed when  $M_x$  and  $CO_x$  are  $\geq 0.3$  at all MAPs during CPB (Fig. 6). An attenuated autoregulation plateau is usually observed. Thus, the “optimal” MAP, defined as the MAP with the lowest  $M_x$ , will be the blood pressure target during CPB, as this point is observed in patients with functional and impaired autoregulation. As blood pressure varies during the usual course of surgery, including during the initiation of CPB, no specific interventions are needed to establish autoregulation indices. Clinicians will have access to  $CO_x$  data only for patients randomized to the Intervention Group.

**The autoregulatory threshold will be defined as the mean arterial pressure at which the mean velocity index increases to  $\geq 0.2$  or cerebral oximetry index increases  $\geq 0.3$ .**

Information regarding the mean arterial pressure at which the lower CBF autoregulatory threshold is detected will be made available to the anesthesiologist, perfusionist, and critical care doctors who are caring for the patients in the Intervention Group before and after surgery. Physicians and perfusionists will be told specifically that a patient has been randomized to the Intervention Group and that his/her mean arterial pressure should be kept higher than that value associated with a mean velocity index  $\geq 0.2$  or cerebral oximetry index  $\geq 0.3$ . During surgery, the mean velocity index will be monitored continuously by the investigative team to confirm that treatments are instituted if mean arterial pressure falls below these limits. These same data will be collected in the Control Group but no specific measures for treating blood pressure will be advised.

At the conclusion of surgery, patient steaming data files will be stored on a portable computer in the ICM+ file. The data files will be transferred to a departmental server with a password-protected file folder specifically designed for this study. Data on the server is backed up daily. The data from each patient will be copied to an excel spread sheet. This data will include the mean arterial pressure from a range of 0 to 115 mmHg and the corresponding mean velocity index and cerebral oximetry index as well as the percentage of time at each blood pressure.

### ***Blood Pressure Management***

To avoid hypotension during surgery, angiotensin converting enzyme inhibitors will not be given on the day of surgery. Patients randomized to the blood pressure Intervention Group will have their mean arterial pressure treated according to the protocol outlined in Appendix A when it is below the lower autoregulatory limits as determined by mean velocity index or cerebral oximetry index. Patients in the Control Group will receive the same treatment, but the lower threshold for treatment will be based on institutional practices and not mean velocity index or cerebral oximetry data. The threshold for treating high blood pressure is not specified and will be based on institutional practices. A

treatment algorithm for treating high blood pressure is provided to ensure consistency in treatments between patients. To avoid a precipitous drop in mean arterial pressure on initiation of CPB, a 100- $\mu$ g bolus dose of phenylephrine will be given intravenously immediately before drainage of blood from the patient to the CPB reservoir. Initiation of CPB will be begun gradually, at no more than 2 L/min, to allow slow equilibration. CPB will be increased by 0.5 L/min increments to the calculated full CPB flow. Phenylephrine boluses (50–100  $\mu$ g) can be given when mean arterial pressure is below the lower limit, until it is stabilized.

Hypotension for periods other than during CPB will be treated by first ensuring adequate cardiac preload with crystalloid or colloid. The decision will be dictated by examination of left and right ventricular end-diastolic areas with transesophageal echocardiography or based on central venous pressure or pulmonary capillary wedge pressure when a pulmonary artery catheter is in place and transesophageal echocardiography is not used. If cardiac filling is normal, as described above, and systemic vascular resistance is low, hypotension will be treated using the same algorithm as that for treating hypotension on CPB. If cardiac preload is adequate but cardiac function is poor (or cardiac index of <2.0 L/min/m^2), epinephrine will be started per hospital standard care. If cardiac function/cardiac index remains depressed, milrinone and dobutamine will be used per hospital standard care. Persistent low cardiac function/cardiac index, including that resulting from right ventricular dysfunction, will be treated according to institutional treatment guidelines.

Patients will be evaluated at screening and sometime between postoperative day 5 and 7 or at hospital discharge (whichever occurs first) with the National Institutes of Health Stroke Scale (NIHSS). The NIHSS is a standardized, validated neurologic examination used in clinical trials to evaluate change in neurologic status. The test quantifies neurologic deficits in 11 categories using a 42-point scale. This testing will be performed by a trained research nurse. Research personnel will be certified for performing the NIHSS using the American Stroke Association's Online NIH Stroke Scale Training Program (<http://asa.trainingcampus.net/uas/modules/trees/windex.aspx>). Patients with a change from baseline in their NIHSS will be referred for evaluation by a neurologist per hospital standard of care by their medical team. An MRI of the brain will be obtained when stroke is likely based on the neurologist's examination. Brain CT imaging will be substituted for MRI when MRI is viewed as clinically contraindicated. Central nervous system infarction will be defined based on the Expert Consensus Statement of the American Heart and Stroke Associations as ischemic injury to the brain, spinal cord, or retina based on pathological, imaging, or other objective evidence of cerebral, spinal cord, or retinal focal ischemic injury in a defined vascular distribution; or clinical evidence of cerebral, spinal cord, or retinal focal ischemic injury based on symptoms persisting for  $\geq$ 24 h or until death, and other etiologies have been excluded. A stroke will be defined as an episode of neurologic dysfunction caused by focal cerebral infarction. An intracerebral hemorrhage will be defined as a focal collection of blood within the brain parenchyma or ventricular system that is not caused by trauma. A transient ischemic

attack is defined as focal arterial ischemia with transient symptoms lasting < 24 h without evidence of infarction by pathology or imaging.

**Delirium Assessment:** Delirium is characterized by an acute-onset, fluctuating disorder in level of consciousness associated with changes in cognition, attention, and perception not explained by pre-existing or evolving dementia. Trained examiners can diagnose delirium and quantify its severity with structured instruments (Appendix C). Examinations are followed by case-by-case adjudication. A Mini Mental Status Exam and Abbreviated Digit Span will be done preoperatively to establish a baseline. Delirium assessments will be made on three of the first four postoperative days using the following tools:

**a.** Confusion Assessment Method (CAM) is a standardized method that is designed to allow trained non-psychiatrists to diagnose delirium. It shows high inter-rater reliability, sensitivity (94–100%), and specificity (90–95%) when compared to the gold standard of psychiatric diagnosis. The CAM diagnostic algorithm is based on assessing the four cardinal features of delirium: 1) acute onset and fluctuating course, 2) inattention, 3) disorganized thinking, and 4) altered level of consciousness.

**b.** Confusion Assessment Method for the Intensive Care Unit (CAM-ICU) is a validated instrument used to diagnose delirium in critically ill intubated patients in the ICU, including those who are non-verbal due to mechanical ventilation. Inter-rater reliability is high (kappa 0.79–0.95), and it has high sensitivity (95–100%) and specificity (89–93%) when compared to the gold standard of psychiatric diagnosis. This test will be used for intubated patients in the ICU.

**c.** Delirium Rating Scale-Revised-1998 (DRS-R-98) is a 16-item scale that has been validated as a measure of delirium severity. Inter-rater reliability is high (interclass correlation coefficient = 0.99), and the scale is one of the few that has been validated against a dementia group.

Trained delirium assessors (authorized research members) will obtain a history of current symptoms from the patient, care providers, and family; review medical records; and perform a mental status exam and cognitive screens that will include the Mini Mental State Exam (MMSE) and abbreviated digit span. This information will be used to rate the CAM, producing a binary outcome for the presence or absence of delirium in the past 24 h. The DRS-R-98, which yields a delirium severity rating, will also be completed. If a patient is unable to respond verbally to questions because of intubation and mechanical ventilation, the CAM-ICU version will be administered. This instrument has sensitivities of 76%–80% and a pooled specificity of 96% in the ICU.

**Neurocognitive Function:** A component of the endpoint of this study is cognitive decline after surgery compared with the patient's baseline. Cognitive testing will be performed within two weeks before surgery, 4–6 weeks after surgery, and 1 year after surgery. Most elective cardiac surgical procedures are performed on patients admitted to the hospital the day of surgery. Assessing baseline cognitive status in patients during an outpatient visit is confounded by time constraints and anxiety that might bias the data and affect enrollment. Nonetheless, we have extensive experience in performing cognitive testing

on the day before cardiac surgery. For patients already admitted to the hospital, cognitive testing and other preoperative assessments will be performed on the ward. For patients who will be admitted the day of surgery, testing will occur either after their preoperative visit with their surgeon or by a separate visit specifically for the purposes of the study. For outpatients, testing before surgery will be at NMH.

Postoperative cognitive testing will be performed at the patient's postoperative surgical clinic visit, in NMH which usually occurs 4–6 weeks after surgery, and again at 1 year after surgery.

Our goal for cognitive testing is not to test hypotheses about specific types of cognitive decline or about injury to specific brain regions. We have selected neuropsychologic tests that assess a number of cognitive domains known to be affected by cardiac surgery. They have the advantage of being standardized. They are also brief and easy to administer and score; the total administration time is approximately 35–45 min. Based on our previous experience, this focused approach is highly feasible for testing surgical patients. The battery is listed in Appendix B and consists of the Rey Auditory Verbal Learning Test, a test of verbal learning and memory; Rey Complex Figure Test, an assessment of visual memory; Controlled Oral Word Association Test, a test of executive functions; Symbol Digits Modalities Test, a test of psychomotor speed and attention control; Trail Making A and B, tests of visuomotor speed, attention, and executive functions; Grooved Pegboard Test, a measurement of fine motor dexterity and speed; Beck Depression Inventory, a self-reported scale of depression symptom severity; and the State-Trait Anxiety Inventory, a measurement of anxiety symptoms. The patients are also evaluated with the SF-36 short form of the RAND Medical Outcomes Study (MOS) health-related quality of life questionnaire. This questionnaire is a multi-item scale that measures 8 health-related concepts: physical function, social function, physical role, emotional role, mental health, energy, pain, and general health perceptions. The standardized scores for each of the 8 quality-of-life domains range from 0 (worst) to 100 (best). The SF-36 has been used in previous studies to assess quality of life in cardiac patients and chronically ill populations. Cognitive decline will be defined as a decrement in performance from baseline to postoperative testing of at least 1 standard deviation (SD) in two or more tests, or 2 SD in one test. It has been shown that this definition is unlikely to classify random test-retest variability as decline but is nonetheless sensitive enough to detect actual postoperative change in cognitive performance.

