## **Detection of Brain Injury**

Brain injury after cardiac surgery has a range of clinical manifestations, including clinical stroke (detected in ~2%–5% of patients) and cognitive decline (reported in 18%–40% of patients, depending on statistical criteria and timing of testing). Cognitive testing has methodologic limitations that lower its sensitivity and specificity for detecting neurologic injury (as opposed to its use for studying the effects of surgery on cognition), including difficulty with distinguishing the confounding effects of preexisting cerebral vascular disease. Moreover, preexisting brain infarction is associated with cognitive impairment, regardless of surgery, thus lowering the likelihood of being able to diagnose further cognitive decrement from new injury or “basement effect.” Nonetheless, our data indicate that cardiac surgery results in changes in cognition indicative of brain injury. Cognitive decline, though, appears to be a transient phenomenon, with most individuals returning to near baseline by 3–6 months after surgery. More controversial is the relationship between perioperative cognitive decline and long-term cognitive decline. Data from our colleagues suggest that the rate of long-term cognitive decline is not different for patients undergoing CABG surgery than it is for patients with documented coronary artery disease undergoing medical management. These findings suggest that the natural progression of cerebral vascular disease, as opposed to the use of CPB per se, is a major determinant of longitudinal decline in cognition after cardiac surgery.

*Understanding the impact of interventions aimed at reducing brain injury from cardiac surgery on long-term cognition may help assess their overall benefit for patient outcome.*

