#### **INCLUSION AND EXCLUSION CRITERIA:**

**Inclusion criteria** will be male or female patients,  $\geq 55$  years old, undergoing primary or re-operative CABG, aortic root replacement and/or valvular surgery that requires CPB (but not undergoing circulatory arrest) who are at high risk for neurologic complications (stroke or encephalopathy) as determined by a Johns Hopkins Encephalopathy Risk score of  $>0.05$ , or Stroke Risk  $> 0.02$ . This prediction algorithm, devised from data analysis by the investigative team, identifies probability of an adverse neurologic outcome based on five patient-related factors: age, prior stroke, diabetes, hypertension, or the presence of a carotid bruit. Women of childbearing potential will have a urine pregnancy test done prior to surgery to insure that they are not pregnant.

Patients will be ineligible for this study if they have any of the following **exclusion criteria**:

1. Contraindication to MRI imaging (e.g., permanent pacemaker, cerebral arterial vascular clips);
2. AST, ALT and Alkaline phosphatase obtained before surgery which is more than twice the upper limit of institutional normal value and which, in the opinion of the principal investigator, is believed to be related to hepatic dysfunction;
3. Chronic renal failure requiring renal dialysis. (Subjects with an estimated glomerular filtration rate  $\leq 60$  mL/min who do not require dialysis may be included in the study. However, these subjects will not receive gadolinium during their MRI/MRA.);
4. Emergency surgery;
5. Inability to attend outpatient visits;
6. Visual impairment or inability to speak and read English; or
7. Female of child bearing capacity with a positive pregnancy test.
8. Individual adults less than 54 years old
9. Prisoners

*The patient will be excluded from further study if an adequate temporal window for TCD monitoring cannot be identified before surgery.*

**STUDY-WIDE NUMBER OF PARTICIPANTS:** Initially we are conducting a 5-year study that includes a 1-month interval for investigator training and start-up, 56 months for enrollment of 280 patients ( $\sim 5$  patients/month), and 3 months for final patient followup testing, data analysis, manuscript preparation, and dissemination of the results (see Rapid Dissemination of Clinical Research). The initial study time line is schematically summarized in Table 2.

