**Aim 1b: To assess whether targeting MAP to a level above an individual's lower CBF autoregulatory threshold during CPB reduces the frequency of cognitive decline 1 year after surgery compared with the use of standard blood pressure management.** In Aim 1, we will test whether the Intervention and Control groups have the same risk of the primary composite neurologic endpoint of stroke, DWI lesion, or cognitive decline 4 to 6 weeks after surgery (i.e., null hypothesis). This will be done using a two-sided test of proportions at 5% significance level. We will first calculate and report the relative risk (RR) of composite neurologic outcome by comparing the Intervention and Control groups without adjusting for any potential confounders (i.e., the unadjusted RR). In addition, we will construct an adjusted estimate of RR using a generalized linear model (GLM) with Poisson distribution and robust standard errors. The candidate models will include study group as the primary independent variable as well as extra- or intracranial arterial stenosis determined by MRA, patient age, gender, and baseline risk factors that are assumed to be highly predictive of the outcome, such as history of hypertension, diabetes, or prior stroke. To assess potential effect modification by cerebral arterial stenosis, age, gender, hypertension, diabetes, or prior stroke (Aim 1a), we will calculate the unadjusted RR stratified by these variables. We will use a test of homogeneity to compare stratum-specific estimates of RR. Finally, we will use the model developed in Aim 1 to report stratum-specific adjusted estimates of RR by introducing appropriate interaction terms of these variables and study group in the GLM model. We will compute the Z-score for the cognitive tests to normalize the distribution to the control data. The individual Z-scores will be combined into an average score and re-normalized. To assess postoperative change in cognitive function for up to 1 year (Aim 1b), we will use population-average marginal models estimated using generalized estimating equations (GEE) with exchangeable working correlation structure. The model will include assessment time with 2 indicator variables for 1 year and 4 to 6 weeks postoperation and baseline as the reference group as well as Intervention Group, and their interaction to test whether postoperative trajectory of cognitive function differs by group.

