In **Aim 5**, we will test the hypothesis that frailty is associated with postoperative delirium. The primary outcome will be the development of delirium at any time, as measured by CAM or CAM-ICU and coded as a binary variable. Secondary outcomes will be delirium severity from the DRS-R-98 scale. Bivariable and multivariable logistic regression analysis will be used to determine if frailty is associated with postoperative delirium. We will also test the hypothesis that frailty is associated with decreased function after cardiac surgery. The primary outcome will be proportion of patients with >1 IADL decline. Secondary outcomes will be change in gait speed and grip strength. Bivariable and multivariable linear and logistic regression analyses will be used. For each of these analysis, covariates to include in the model will be selected using a priori evidence, and may include age, gender, race, baseline cognitive status, education, medications, and

type of surgery. We will also consider propensity score analysis to account for important confounding.

**Aim 6:** *To determine whether depth of anesthesia in frail patients is a modifiable risk factor for delirium and functional decline after cardiac surgery.*

In **Aim 6**, we will compare cumulative time of BIS<45 in frail vs. non-frail patients using bivariable and multivariable linear regression. The cumulative time of BIS<45 will also estimate the amount of potential anesthetic overdose in all patients.

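### The supplementary adjusted RR of the primary composite does not prespecify the baseline cognitive score, although one component of the composite is a fall from that score

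*Combined protocol and SAP*

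**What the plan says.** All references are to the combined protocol and SAP.

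- **Endpoint.** The Neurocognitive Function paragraph states: "A component of the endpoint of this study is cognitive decline after surgery compared with the" patient's baseline. That paragraph defines decline as a drop of 1 SD in two or more tests or 2 SD in one. The Statistical Analysis Plan section defines it as a fall of more than 0.3 in the composite Z-score at 4 to 6 weeks. Both are falls from the patient's own preoperative performance.
- **Timing.** Baseline testing takes place in the two weeks before surgery. Patient Randomization places allocation after anaesthesia induction and mentions no stratification factor.
- **Primary test (Study Statistics, Aim 1).** "This will be done using a two-sided test of proportions at 5% significance level". The unadjusted RR is calculated and reported first.
- **Adjusted RR (same section).** "In addition, we will construct an adjusted estimate of RR using a generalized linear model (GLM) with Poisson distribution and robust standard errors". The models are described as candidates. They contain study group, arterial stenosis on MRA, and "patient age, gender, and baseline risk factors that are assumed to be highly predictive of the outcome", with hypertension, diabetes and prior stroke given as examples. Baseline cognition is not among them.
- **Other covariates.** The Statistical Analysis Plan section will explore as potential confounders variables that predict outcome and are distributed differently between the arms, and will let the results guide model selection.
- **Aim 5.** For the frailty analyses, covariates "may include age, gender, race, baseline cognitive status, education, medications, and" type of surgery.

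**The concern.** A patient with a high preoperative score has more room to fall and will tend to regress toward the mean. A patient with a low score has less room. The plan recognises the second half of this: in Detection of Brain Injury it says that pre-existing infarction goes with cognitive impairment, "lowering the likelihood of being able to diagnose further cognitive decrement from new injury". The baseline score is therefore expected to predict who is classed as declining, even when surgery has done no harm.

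Naming such a variable in advance does two things for a randomised comparison. It recovers some precision, and it removes the part of any chance baseline imbalance that feeds into the endpoint. Letting it in after outcomes and arm differences have been examined gives the same model a data-driven origin, which makes the adjusted RR harder to defend. At stake is the precision and credibility of the adjusted RR only.

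**Working it through.** **1. The plan's sample size.** Inputs from the sample-size text: 45% in control, a 40% reduction (27%), two-sided 5%, 80% power.

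- Mean proportion 0.36; 2 × 0.36 × 0.64 = 0.4608 (root 0.679); 0.45 × 0.55 + 0.27 × 0.73 = 0.4446 (root 0.667).
- n = (1.96 × 0.679 + 0.842 × 0.667)² / 0.18² = 110.5, so 111 per arm. With the continuity correction it is 122.

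The stated 122 is reproduced. It assumes no covariate adjustment, so the covariate list does not affect it.

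**2. How baseline drives the decline component.** Input: within-patient correlation r = 0.7, from the plan's power calculation for the combined Z-score. Assumptions: normal scores, SD 1 at both times, no true change. With baseline z,

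P(decline | z) = Φ[(-0.3 + (1 - r)z) / √(1 - r²)], and √(1 - 0.49) = 0.714.

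| z | Argument | P(decline) |
|---|---|---|
| +1 | 0 / 0.714 = 0 | 50% |
| 0 | -0.3 / 0.714 = -0.42 | 34% |
| -1 | -0.6 / 0.714 = -0.84 | 20% |

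For r from 0.6 to 0.8 the range is 43-55% at +1 SD and 19-20% at -1 SD. Under the other definition (1 SD in two tests or 2 SD in one), taking 10 battery scores and an assumed inter-test correlation of 0.3, the figures are about 36% and 15%.

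**3. From component to composite.** Hold the control composite at 45% and let cognitive decline be 18%, 25% or 40% (the plan's background range is 18-40%). Assume the other components are independent of decline and of baseline. Their combined rate is then 1 - 0.55/0.82 = 33%, 1 - 0.55/0.75 = 27% or 1 - 0.55/0.60 = 8%. The correlation of change with baseline is -√((1 - r)/2) = -0.39 at r = 0.7.

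| Decline rate | R² of composite on baseline, r = 0.7 | r = 0.8 | r = 0.5 |
|---|---|---|---|
| 18% | 1.9% | 1.2% | 3.1% |
| 25% | 3.3% | 2.2% | 5.5% |
| 40% | 7.5% | 5.1% | 12.7% |

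A separate simulation that applied the plan's two decline rules directly, with DWI lesion rates of 26-56%, gave R² of 1.1-4.7%.

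**4. Check in the planned model.** Modified Poisson with robust SE, 122 per arm, r = 0.7, 1,500 simulated trials per scenario:

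- 18% decline: mean SE of log RR falls from 0.181 to 0.179.
- 40% decline: it falls from 0.181 to 0.175.
- The RR stays at about 0.60 with and without the covariate.

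**5. Chance imbalance.** The SD of the arm difference in baseline Z is √(2/122) = 0.128, so a 2-SD imbalance is 0.256. The slope of P(decline) at the mean is 0.153 per SD, which gives 0.256 × 0.153 = 3.9 points on the decline component. On the composite, with DWI lesions at 56% or 26%, this is 3.9 × 0.44 = 1.7 or 3.9 × 0.74 = 2.9 points. Under the step 3 model, a 0.25 SD imbalance gives 1.7-3.4 points. The planned difference is 45 - 27 = 18 points.

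**The case against.** The case against has several parts, and most of it stands.

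- **A reader might infer that the primary result loses precision.** It does not. The test and the first-reported RR are unadjusted by design, and the adjusted RR is additional. Chance imbalance is already covered by the error rate of the unadjusted test.
- **A reader might infer that the plan excludes the score.** The text does not support that. The models are candidates and the risk factors are examples. The exploratory rule could admit the score, and it does not say that a variable enters only if the arms differ. The gap is one of prespecification.
- **A reader might infer an inconsistency with Aim 5.** The wording there is permissive ("may include age, gender, race, baseline cognitive status, education, medications, and" surgery type), and the question is observational, so confounding has to be handled differently. It shows only that the authors think baseline cognition is relevant.
- **A reader might call baseline cognition the leading predictor.** Nothing in the documents ranks it so. The eligibility risk score uses age, prior stroke, diabetes, hypertension and carotid bruit, and the adjusted model names the first four.
- **Independence from lesions is doubtful.** The Background section says prior infarction raises the risk of new injury, and Detection of Brain Injury links it to impaired cognition. A low baseline could lower measured decline and raise lesion risk, and the two would partly cancel in the composite.

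What remains is that a pre-randomisation variable built into the endpoint definition is left unnamed, and the described way of adding it looks at outcome and imbalance first.

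**Conclusion.** The point holds as a low-priority improvement to a supplementary analysis. The adjusted RR of the composite does not prespecify the baseline cognitive score, although that score enters the definition of one component.

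The gradient within the decline component is clear: 50% against 20% across ±1 SD at r = 0.7. Its effect on the composite is modest. Variance falls by roughly 1-8% for r of 0.7-0.8, and by up to about 13% only if r is 0.5 and decline is 40%. An unlucky imbalance would move the composite by about 2-3 points out of 18. These figures rest on a linear normal model, no true change in step 2, and baseline independent of lesions and stroke. If a low baseline raises lesion risk, the gain could be smaller or larger. The validity of the unadjusted test, its type I error and the sample size are not in question.

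**What to change.** In Study Statistics, Aim 1, state that the Poisson model for the adjusted RR includes the baseline composite cognitive Z-score as a continuous, fixed covariate, whatever imbalance is observed. Keep the unadjusted test of proportions as the primary test.

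Two further covariates could be fixed in the same way, but their gain has not been quantified. One is type of surgery in the Aim 1 model, since the trial enrols patients "undergoing primary or re-operative CABG, aortic root replacement and/or valvular surgery that requires CPB". The other is the preoperative MMSE in the adjusted RR of delirium under Aim 4, where no covariate is named.

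The cost is one sentence and one degree of freedom for the main change. The score is already collected. A patient without it cannot be assessed for cognitive decline, so few patients with complete endpoint data should be lost from the adjusted model.
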